12.2.2 ELICITING ADVERSE EVENT INFORMATION

Adverse events will be recorded from the time the participant signs the Informed Consent Form until 14 days after each visit.

12.2.3 ASSESSMENT AND DOCUMENTATION OF ADVERSE EVENTS

The project manager is responsible for recording all adverse events, regardless of their relationship with the exposure, with the following exceptions:

- Conditions that are present at screening and do not deteriorate will not be considered adverse events.
- Abnormal laboratory values will not be considered adverse events unless deemed clinically significant by the investigator and documented as such.

Adverse events will be recorded using the Adverse Events Report Form, which will record:

- A description of the AE;
- The onset date, duration, date of resolution;
- Severity (mild, moderate or severe);
- Seriousness (i.e. is it an SAE?)
- Any action taken (e.g. treatment, follow-up tests);
- The outcome (e.g. recovery, death, continuing, worsening);
- The likelihood of the relationship of the AE to the exposure being investigated (e.g. Unrelated, Possible, Probable, Definite).
- Whether and when reported to the HREC

All AEs will be followed to adequate resolution.

12.2.4 SERIOUS ADVERSE EVENT REPORTING

Any SAE occurring in a study participant will be reported to study site. The SAE reporting form will be completed, signed and submitting by an investigator. All SAE reporting forms will be reported to the HREC by email to [contact] in line with the Melbourne Health Research policy.

All SAEs and AESIs, pregnancy and overdose, regardless of the investigator's causality must be reported to Sanofi within one (1) business day of becoming aware of the event.

Sanofi Global Pharmacovigilance
Email: [contact] or Fax: to [name]

And copy in the Australian Sanofi Product Safety Department:
Email: [contact]

All SAEs should be submitted to the appropriate Regulatory Authority (TGA) in accordance with the applicable timelines and reporting requirements.

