1 STUDY SYNOPSIS

Provide brief information

Title:	Investigation and Comparison of the Antibody Response initiated by Recombinant, Cell-Based and Egg-Based Influenza Vaccines
Short Title:	Immunogenicity trial of 3 influenza vaccines
Design:	Randomized controlled trial
Study Centre:	National Centre for Infectious Diseases (NCID), Singapore; WHO Collaborating Centre for Reference and Research on Influenza
Hospital:	National Centre for Infectious Diseases Research Clinic
Study Question:	Does recombinant vaccine result in a better antibody response than either standard egg-grown vaccine or cell-grown vaccine?
Primary objective:	To assess whether vaccination with recombinant quadrivalent influenza vaccine (QIV-R) results in a better antibody response against A(H3N2) viruses than either standard egg-grown vaccine (QIV-E) or cell-based vaccine (QIV-C) as measured by post-vaccination geometric mean titre from the haemagglutination inhibition assay
Secondary objectives	
1. To estimate whether antibody responses to all 4 vaccine antigens are greatest in participants who received QIV-R and least in participants who received QIV-E, and if this reflects greater cell- to egg-grown antibody titre ratios.2. To estimate whether QIV-R induces antibodies against a greater genetic and antigenic range of A(H3N2) viruses than QIV-C and QIV-E.3. To estimate whether prior vaccination history has less effect on antibody responses induced against all 4 vaccine antigens by QIV-R compared with QIV-C and QIV-E.4. To estimate whether antibody titres against all 4 vaccine antigens are better maintained up to 12 months after vaccination with QIV-R compared with QIV-C and QIV-E.5. To estimate whether QIV-R induces higher frequencies of HA reactive B cells and/or B cells with different HA cross-reactivity profiles and phenotypes compared with QIV-C and QIV-E.6. To assess whether QIV-R offers better protection against infection compared with QIV-C or QIV-E.
Inclusion Criteria:	
1. Aged ≥ 21 years and < 50 years.2. Able to provide informed consent

Study Name: Immunogenicity trial of 3 influenza vaccine [VAP3]

Protocol Number: 2021.247

DSRB Ref Number: 2022/00275

Version & date: version 2.0, dated 27 Oct 2022

Page 6 of 38

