4.2.1 STUDY OVERVIEW

This study will be conducted in 360 adults, aged 21-49 years in Singapore to generate immunogenicity data. It will be a randomized, modified double-blind study comparing the immunogenicity of recombinant quadrivalent influenza vaccines (QIV-R) against egg-based (QIV-E), and cell-based (QIV-C) vaccines. This study is powered to primarily assess the immunogenicity (as assessed by hemagglutination inhibition (HAI) geometric mean titres (GMTs) at 14-21 days post-vaccination) of QIV-R compared with QIV-E, and will also assess QIV-R compared with QIV-C.

Given the acceptable safety data generated from the millions of doses of licensed QIV-R administered in the US and elsewhere and the fact that we will source this product from the US, it is considered that the risk/benefit ratio is appropriate for the conduct of a clinical study with QIV-R.

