7.2 JUSTIFICATION OF THE STUDY DESIGN

The objectives of this study will be to assess whether vaccination with QIV-R results in a better immune response towards vaccination compared with either QIV-E or QIV-C.

The vaccines QIV-C and QIV-R used in this study are not licensed in Singapore. However, given the acceptable safety data generated from the millions of doses of QIV-R administered in the USA (under the tradename Flublok Quadrivalent), and the fact that this product will be sourced from the US, we consider that the risk/benefit ratio is appropriate for the conduct of a clinical study with QIV-R.

Some data already exist comparing QIV-R with QIV-E and QIV-C; however early formulations (pre-2013) of QIV-R were susceptible to the formation of disulphide cross-links, resulting in decreased potency during storage (loss of up to 50% potency). This was rectified through the addition of low concentrations of a reducing agent, sodium thioglycolate (STG), in combination with citrate that reduced the rate of potency loss by up to 20-fold (15, 16). HA instability would have led to suboptimal vaccine being used in clinical trials pre-2014 and could explain the initial need for an increased antigen load (45ug / strain), it could also explain why earlier results failed to show any obvious superiority over traditional vaccines. Therefore, new data are required to assess the immunogenicity of this QIV-R over QIV-E and QIV-C.

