7.4.5 SAFETY MONITORING

Participants will be observed for 15 minutes after vaccination for adverse events (AEs), consistent with usual vaccination practices. Participants are asked to contact the project manager to report an AE / SAE throughout the study period. Additionally, participants will be asked if they have experienced an AE at each study visit. See Section 12 for further information about the collection of AE data.

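### Section 12.2.4 names no Singapore ethics board or regulator as a recipient of SAE reports, although every participant is in Singapore; the AE recording period in 12.2.2 is also ambiguous

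*Combined protocol and SAP*

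**What the plan says.** **Where the trial takes place.** The synopsis gives the study centres as "National Centre for Infectious Diseases (NCID), Singapore; WHO Collaborating Centre for Reference and Research on Influenza", with the NCID research clinic as the hospital. Section 4.2.1 states: "This study will be conducted in 360 adults, aged 21-49 years in Singapore". The page footer carries "DSRB Ref Number: 2022/00275". Section 7.2 adds: "The vaccines QIV-C and QIV-R used in this study are not licensed in Singapore".

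**Where SAE reports go.** Section 12.2.4 has each SAE reported to the study site. It then sends the reporting forms to an HREC "in line with the Melbourne Health Research policy". SAEs, AESIs, pregnancies and overdoses go to Sanofi's global pharmacovigilance group within one business day, with a copy to its Australian product safety department. On regulators it says: "All SAEs should be submitted to the appropriate Regulatory Authority (TGA"; no other authority is named. The AE form in 12.2.3 records whether and when the HREC was told, and section 9.1 has code breaks notified to the HREC.

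**When AEs are recorded.** Section 12.2.2 records AEs from signature of consent "until 14 days after each visit". Section 7.4.5 says "Participants are asked to contact the project manager to report an AE / SAE throughout the study period", and also has participants asked about AEs at every visit. Section 12.2.3 makes the project manager responsible for recording all AEs, with two exceptions, neither of which concerns timing. The schedule in 7.3 has SAEs and AESIs collected throughout the study.

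**The concern.** Site staff will follow the SAE section when an event happens. Followed literally, it takes a report from a Singapore participant to Australian bodies and the manufacturer, and gives no instruction to inform the ethics board or regulator with oversight of the Singapore site. That matters more than usual here because two of the three products are not licensed in Singapore.

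The AE recording period is a lesser matter. If staff apply 12.2.2 in different ways, capture of non-serious AEs will depend on who is recording. That would make the safety tables incomplete in a way that is hard to describe afterwards.

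**Working it through.** **SAE routing.** The plan gives no figure to reproduce, so this is a comparison of recipients.

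| Recipient in 12.2.4 | Singapore body? |
|---|---|
| Study site | Yes, but this is an internal step |
| HREC, under Melbourne Health policy | Not identified as one; the policy points to Australia |
| Sanofi global pharmacovigilance | No (manufacturer) |
| Sanofi's Australian product safety department | No (manufacturer) |
| Regulator: TGA | No |

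The rest of the available text does not fill the gap. Sections 9.1 and 12.2.3 also refer only to the HREC, and the DSRB appears only in the footer. The gap concerns every participant: 6 cells × 60 = 360 (table in 13.2). The 2 × 120 = 240 participants allocated to QIV-C or QIV-R are context for why local oversight matters, and do not measure the routing gap.

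**AE recording period.** Inputs from 7.3 and 8.4: V1 on D1; V2 on D14 (+7 days); V3 on D150 (±30 days); V4 on D330 (±30 days).

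*Narrow reading: each visit opens a window that closes 14 days later.*

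- Nominal days. Windows close at D1 + 14 = D15, D14 + 14 = D28, D150 + 14 = D164 and D330 + 14 = D344.
  - Uncovered: D29–D149, 149 − 29 + 1 = 121 days; D165–D329, 329 − 165 + 1 = 165 days.
  - Total 121 + 165 = 286 of 330 days, or 87%.
- Days uncovered whatever the in-window visit dates.
  - Latest V2 is D21, and D21 + 14 = D35. Earliest V3 is D120. Uncovered: D36–D119, 84 days.
  - Latest V3 is D180, and D180 + 14 = D194. Earliest V4 is D300. Uncovered: D195–D299, 105 days.
  - Total 84 + 105 = 189 days.
- Individual totals at the edges of the windows.
  - V2 D21, V3 D120, V4 D300: D16–D20 (5) + D36–D119 (84) + D135–D299 (165) = 254 of 300 days (85%).
  - V2 D14, V3 D180, V4 D360: D29–D179 (151) + D195–D359 (165) = 316 of 360 days (88%).

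*Continuous reading: recording starts at consent and runs on to 14 days after the last visit.* On nominal days that is up to D344, so 0 of 330 days are uncovered.

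The sentence in 12.2.2 has one start point and does not say whether recording pauses between visits, so it does not settle which reading applies. On the continuous reading it agrees with 7.4.5 and 12.2.3 up to the last visit; on the narrow reading it conflicts with both. SAEs and AESIs are outside this question, because 7.3 collects them throughout.

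**The case against.** **On routing.** The study site is in Singapore and hears of every SAE. The phrase about the appropriate authority is generic. The HREC's address is removed, so its identity is inferred from the Melbourne policy. The text available for review lacks the opening pages and jumps from section 2 to section 4, so a local duty stated there cannot be excluded. Local rules may in any case require reporting.

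A reader might infer that the Singapore authorities would not be told of SAEs. The documents do not support that: silence in the protocol does not show what the site will do. What stands is narrower. The only regulator named is the TGA, the only ethics policy named is Melbourne's, and a local duty stated elsewhere would still have to be reconciled with 12.2.4.

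**On the AE period.** A reader might infer that AE recording stops between visits, and that events in between are lost for every participant. That needs the narrow reading and also a limit on onset date. Section 12.2.2 governs when AEs are recorded and sets no onset limit. An event between visits that is disclosed at V3 or V4 would be recorded at the visit, inside even the narrow window, and the form in 12.2.3 captures its onset date. The day counts therefore measure time outside a recording window and do not count lost events. This objection largely succeeds: what remains is an ambiguity affecting non-serious AEs.

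**Conclusion.** The routing point holds. Section 12.2.4 gives an external SAE route with no named Singapore ethics board or regulator, in a trial whose 360 participants are all in Singapore. This rests on the available text and on two assumptions, since the glossary expands neither abbreviation: that the DSRB reference belongs to the ethics board overseeing the Singapore site, and that the TGA is the Australian regulator.

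The AE recording point is secondary and is one of ambiguity. Depending on the reading, between 0 and 286 of 330 nominal days fall outside recording. On the narrow reading, 189 days are uncovered whatever the in-window visit dates. These figures apply to non-serious AEs only. A claim that SAE or AESI capture is interrupted would contradict 7.3.

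Neither point affects the immunogenicity primary analysis or the sample size. Both should be corrected because they bear on participant oversight and on the completeness of the safety data.

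**What to change.** 1. In 12.2.4, name as SAE recipients the ethics board that holds the DSRB reference and the Singapore regulator. Keep the Melbourne HREC, the Australian Sanofi department and the TGA where the sponsor confirms that they apply.
2. Make the HREC references in 9.1 (code breaking) and 12.2.3 (AE form) say which board is meant, consistent with 12.2.4.
3. Reconcile 12.2.2 with 7.3, 7.4.5 and 12.2.3 so that one AE recording period applies, and say whether events that arise between visits and are disclosed at the next visit are recorded. The choice of period is for the sponsor.

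The cost is a protocol wording amendment, a matching change to the AE form, and copies of SAE reports to the local bodies. No change to visits, sample size or analysis is needed.

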12.3 HANDLING OF WITHDRAWALS

Participants may withdraw from the study at any time for any of the following reasons: participant has chosen to withdraw from the study, protocol violation, or participant has experienced an adverse event.

Study Name: Immunogenicity trial of 3 influenza vaccine [VAP3]

Protocol Number: 2021.247

DSRB Ref Number: 2022/00275

Version & date: version 2.0, dated 27 Oct 2022

Page 27 of 38

Information collected to that point will be kept unless the participant explicitly requests otherwise. This information will be used for comparison with participants who complete all study procedures.

All participants will be included in the study analyses, so it is important to have information on as many participants as possible. If a participant wishes to withdraw from the study, every reasonable effort will be made to complete a final evaluation of participants who exit the study early and the reason(s) for withdrawals will be recorded in the participant's study records.

12.4 REPLACEMENTS

The sample recruited allows for some attrition. However, we will attempt to replace participants who fail to attend their first follow-up (V2).

12.5 POTENTIAL BENEFITS TO SUBJECTS

All participants will receive a quadrivalent influenza vaccination. Participants should benefit from coverage against influenza and may be less likely to catch influenza or develop complications during the study period.

Participants will be vaccinated against the influenza A/H1N1, A/H3N2 and the B strains from both the Victoria and Yamagata lineages chosen and recommended by WHO for the composition of QIVs for the 2022–2023 NH season.

Regarding immunogenicity, QIV-R is expected to induce a higher immune response against the 4 influenza strains compared to QIV-C or QIV-E. Therefore, QIV-R is likely to bring an increased benefit versus QIV-C or QIV-E in terms of immunogenicity against the 4 influenza strains with a risk-benefit profile that is expected to be favourable.

13 STATISTICAL METHODS

13.1 RANDOMISATION

Subjects will be stratified based on history of vaccination and randomised into the three vaccine groups using a block-randomisation scheme.

13.2 SAMPLE SIZE ESTIMATION & JUSTIFICATION

The sample size is calculated considering the primary objective to test whether QIV-R offers superior immunogenicity independent of vaccination history. Our estimates for post-vaccination HI titres are based on a study among elderly adults in Hong Kong, comparing QIV-R and QIV-E (20) and is similar to the estimated sample size based on similar HI titres in a study of 18-49 year olds (21).

A sample was simulated under the following model, informed by the published estimates:

$$titre_{t=2} = titre_{t=1} + vax_R + vax_C + priorvax + vax_R \times priorvax + vax_C \times priorvax$$

(titre_{t=2} = post vaccination log titre; titre_{t=1} = post-vaccination log titre for QIV-E infrequent vaccination; vax_R = QIV-R vaccinated; vax_C = QIV-C vaccinated)

For the test of a superior A(H3N2) response among vaccinees receiving QIV-R versus QIV-E or QIV-C (one-sided test for the parameter vax_{recomb}) and assuming $\alpha=0.05$, $\beta=0.2$, the sample needed to test these effects is around 55 per arm per vaccination history. Accounting for 10% attrition, the target sample for recruitment will be 60 per arm per vaccination history.

	Infrequently vaccinated	Frequently vaccinated	Total
QIV-R	60	60	120
QIV-E	60	60	120
QIV-C	60	60	120
Total	180	180	360

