13.3 POWER CALCULATIONS

Power calculations were simulation-based. The following model was used for the simulations:

$$\logtitre_{t=2} = b_0 + b_{baseline} \logtitre_{t=1} + b_{priorvax} priorvax + b_C vax_C + b_R vax_R + b_{C-add} vax_C priorvax + b_{R-add} vax_R priorvax + e$$

The following table contains the interpretation of all model terms.

Term	Interpretation
logtitre _{t=2}	Post-vaccination log-titre.
b ₀	Expected post-vaccination log-titre for baseline log-titre 0, infrequent prior vaccination, vaccinated with QIV-E.

b_{baseline}	Expected increase in the post-vaccination log-titre for a 1-unit increase in the pre-vaccination log-titre. Adjusted for prior vaccination frequency and vaccine received.
$\log\text{titre}_{t=1}$	Pre-vaccination log-titre.
b_{priorvax}	Expected difference in the post-vaccination log-titre between the frequently and infrequently vaccinated. Adjusted for baseline titre.
priorvax	0=Infrequent prior vaccinations. 1=Frequent prior vaccinations and vaccine received.
b_C	Expected difference in post-vaccination log-titre between QIV-E and QIV-C. Adjusted for baseline titre and prior vaccination frequency.
vax_C	0=Not vaccinated with QIV-C. 1=Vaccinated with QIV-C.
b_R	Expected difference in post-vaccination log-titre between QIV-E and QIV-R vaccine. Adjusted for baseline titre and prior vaccination frequency.
vax_R	0=Not vaccinated with QIV-R. 1=Vaccinated with QIV-R.
$b_{C\text{-add}}$	Expected additional effect of QIV-C in the frequently vaccinated.
$b_{R\text{-add}}$	Expected additional effect of QIV-R in the frequently vaccinated.
e	Random error

The following table contains the values used for the parameters in the model (subsequent tables will show deviations if there are any).

Term	Value
b_0	1.1
b_{baseline}	0.8
b_{priorvax}	-0.2
b_C	0.25
b_R	0.5
$b_{C\text{-add}}$	0
$b_{R\text{-add}}$	0.2

In each simulation there was an equal number of subjects in each arm and vaccination history group. Baseline log-titres were simulated from $N(3.7, 1)$ which produced a distribution representative of the baseline titre data of published studies. The error term was sampled from $N(0, 1)$ which produces post-vaccination titre distribution representative of published studies.

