The model simulates a subject's post-vaccination titre given their pre-vaccination titre, prior vaccination status (frequent or infrequent) and the vaccine they were given (QIV-R, QIV-C, QIV-E). The effect of the vaccines was allowed to vary between frequently and infrequently vaccinated.

Simulations were performed with different per-group sample sizes and different effects of QIV-R (b_R). For the purposes of fitting the model to the simulated data, all titres were censored to the appropriate interval (<10, 10-20, 20-40 up to 5260-10240 on the original titre scale) to simulate real measurements. The model was then fit using the midpoints of the intervals except <10 which was censored to 5 (as it would be for real data).

There were 5000 simulations for each sample size and value of b_R . Each simulated dataset was used to fit a model (the same one that was used to simulate it). The primary outcome measure was taken to be the effect of the QIV-R as compared to the QIV-E (i.e., the expected difference in post-vaccination log-titres between the QIV-R and QIV-E,) which corresponds to the b_R parameter in the model. A one-sided and a two-sided test was performed on the b_R estimate for each simulation. The "power" is the proportion of simulated studies that showed that b_R is significantly greater than 0. The results are in the table below.

Per-arm per-vaccine history sample size	True b_R (expected ratio between QIV-R and QIV-E)	Proportion with significant (one-sided) positive b_R	Proportion with significant (two-sided) positive b_R
50	0.5 (1.65)	0.772	0.665
55	0.5 (1.65)	0.810	0.712
60	0.5 (1.65)	0.832	0.741
70	0.5 (1.65)	0.889	0.807
80	0.5 (1.65)	0.920	0.858
200	0.25 (1.28)	0.775	0.676
220	0.25 (1.28)	0.810	0.717
240	0.25 (1.28)	0.834	0.742

Power of 80% can be achieved (for a one-sided test) with approximately 55 subjects per arm/per vaccine history given the true effect of 0.5 (true expected ratio 1.65). The total sample required would be approximately 330 subjects. This equates to 74% power for a two-sided test.

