13.4 STATISTICAL ANALYSES

Study Name: Immunogenicity trial of 3 influenza vaccine [VAP3]

Protocol Number: 2021.247

DSRB Ref Number: 2022/00275

Version & date: version 2.0, dated 27 Oct 2022

Page 31 of 38

The stratification variable of vaccination history will be included as a covariate in models for all primary and secondary objectives.

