13.4.1 PRIMARY OBJECTIVE

To assess whether vaccination with recombinant quadrivalent influenza vaccine (QIV-R) results in a better antibody response against A(H3N2) viruses than either standard egg-grown vaccine (QIV-E) or cell-based vaccine (QIV-C) as measured by post-vaccination geometric mean titre from the haemagglutination inhibition assay

Post-vaccination GMTs will be calculated for each group using the model described in 13.3, in which the outcome is an individual's post-vaccination titre, estimated given their pre-vaccination titre, prior vaccination status (frequent or infrequent) and the vaccine they were given (QIV-R, QIV-C, QIV-E). A t-test (on a model parameter) will be used to assess statistical significance of the effects of QIV-R versus QIV-E and QIV-C.

13.4.2 SECONDARY OBJECTIVE 1

To estimate whether antibody responses to all 4 vaccine antigens are greatest in participants who received QIV-R and least in participants who received QIV-E, and if this reflects greater cell- to egg-grown antibody titre ratios.

The post-vaccination vs pre-vaccination **log-titre difference** (geometric mean ratio) will be compared using linear regression with the explanatory variable being the type of vaccine (reference QIV-E, separate parameter for QIV-R and QIC-C). A t-test will be used to assess statistical significance of the effects of QIV-R and QIC-C (as compared to reference) as well as the difference in those effects.

The post-vaccination **seropositivity** (coded as 1 if the post-vaccination titre is at least 40, 0 otherwise) will be compared using logistic regression with the explanatory variable being the type of vaccine (reference QIV-E, separate parameter for QIV-R and QIC-C). A t-test will be used to assess statistical significance of the effects of QIV-R and QIC-C (as compared to reference) as well as the difference in those effects.

Seroconversion (coded as 1 if the post/pre vaccination titre ratio is at least 4, 0 otherwise) will be compared using logistic regression with the explanatory variable being the type of vaccine (reference QIV-E, separate parameter for QIV-R and QIC-C). A t-test will be used to assess statistical significance of the effects of QIV-R and QIC-C (as compared to reference) as well as the difference in those effects.

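### The 80% power in 13.2 for QIV-R against QIV-C was never calculated: 13.3 tabulates only QIV-R vs QIV-E in the infrequently vaccinated, and its 74% two-sided figure is the row for 60 per cell, not 55

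*Combined protocol and SAP*

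**What the plan says.** Section 13.2 gives the purpose of the sample size as to "test whether QIV-R offers superior immunogenicity independent of vaccination history". It then says: "For the test of a superior A(H3N2) response among vaccinees receiving QIV-R versus QIV-E or QIV-C", one-sided with alpha 0.05 and beta 0.2, "the sample needed to test these effects is around 55 per arm per vaccination history". Allowing for 10% attrition, the target is 60 per cell, 360 in total.

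Section 13.3 describes the simulation behind this. The model has terms for baseline titre, prior vaccination (0 = infrequent), QIV-C, QIV-R, and both vaccine-by-history interactions. The same model was fitted to each simulated dataset. On what was tested, 13.3 says: "The primary outcome measure was taken to be the effect of the QIV-R as compared to the QIV-E", meaning the parameter b_R. The term table describes b_R as: "Expected difference in post-vaccination log-titre between QIV-E and QIV-R vaccine. Adjusted for baseline titre and prior vaccination frequency". Every row of the power table is for b_R. After naming 55 per cell and about 330 in total, the section closes: "This equates to 74% power for a two-sided test".

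Section 6.1 lists two differences under the primary objective, QIV-R vs QIV-E and QIV-R vs QIV-C, each adjusted for vaccination history and baseline titre. Section 4.2.1 says the study is powered primarily for QIV-R vs QIV-E and will also assess QIV-C.

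For the analysis, 13.4 states: "The stratification variable of vaccination history will be included as a covariate in models for all primary and secondary objectives". Section 13.4.1 states: "Post-vaccination GMTs will be calculated for each group using the model described in 13.3", followed by a t-test on an unnamed model parameter for QIV-R against each comparator. Section 13.4.4 adds a vaccine-by-history interaction for secondary objective 3.

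**The concern.** There are three linked problems.

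1. The power claim in 13.2 covers QIV-C, but the calculation does not. The simulation contains a QIV-C arm (b_C = 0.25), yet no power for QIV-R vs QIV-C is reported.

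2. The tabulated parameter is not the primary estimand. With interactions in the model and infrequent coded 0, b_R is the QIV-R vs QIV-E difference among the infrequently vaccinated. Describing it as adjusted for vaccination frequency is wrong for that model, and it does not match 6.1 or the aim in 13.2. Section 13.4.1 carries the ambiguity into the analysis: it refers back to the interaction model but does not name the contrast.

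3. The two-sided power in the closing sentence of 13.3 does not match the row of the table it refers to.

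At stake is what the trial can claim about QIV-C. Depending on which contrast is tested, power for that primary comparison is either close to the stated 80% or less than half of it. An unnamed contrast could also be chosen after the data are seen.

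**Working it through.** **Inputs (13.3).** Baseline log-titre N(3.7, 1); error N(0, 1); b_0 = 1.1; b_baseline = 0.8; b_priorvax = -0.2; b_C = 0.25; b_R = 0.5; b_C-add = 0; b_R-add = 0.2. Cells are equal in size. Titres are grouped into two-fold intervals and replaced by midpoints, with values below 10 set to 5. Logs are natural, since 0.5 is shown as a ratio of 1.65. Alpha is 0.05.

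**True differences under these values**

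- QIV-R vs QIV-E, infrequent: b_R = 0.50
- QIV-R vs QIV-E, averaged over history: b_R + b_R-add/2 = 0.50 + 0.10 = 0.60
- QIV-R vs QIV-C, infrequent: b_R - b_C = 0.50 - 0.25 = 0.25
- QIV-R vs QIV-C, averaged over history: (b_R - b_C) + (b_R-add - b_C-add)/2 = 0.25 + 0.10 = 0.35

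**Reproducing the plan's table.** The 13.3 model was re-simulated with the titre grouping (10,000 runs per setting, Monte Carlo SE at most 0.005). For b_R, one-sided / two-sided:

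| Per cell | Plan's table | Re-simulated |
|---|---|---|
| 55 | 0.810 / 0.712 | 0.812 / 0.713 |
| 60 | 0.832 / 0.741 | 0.829 / 0.740 |

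The history-averaged QIV-R vs QIV-E contrast gives over 0.99 at 55 per cell. The table can therefore only be the infrequent-stratum parameter.

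**All four contrasts at 55 per cell**

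| Contrast | Difference | One-sided | Two-sided |
|---|---|---|---|
| QIV-R vs QIV-E, infrequent (b_R) | 0.50 | 0.812 | 0.713 |
| QIV-R vs QIV-E, averaged | 0.60 | 0.996 | 0.991 |
| QIV-R vs QIV-C, infrequent | 0.25 | 0.350 | 0.241 |
| QIV-R vs QIV-C, averaged | 0.35 | 0.803 | 0.703 |

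A fit with history as a covariate and no interaction gives the same powers as the averaged contrasts (0.996 / 0.991 and 0.803 / 0.703). Using geometric midpoints instead of arithmetic ones changes little: 0.352 / 0.247 for QIV-R vs QIV-C infrequent and 0.796 / 0.702 averaged.

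**Check by formula.** Power is approximately Φ(difference/SE - z), with z = 1.645 one-sided and 1.960 two-sided. The simulated SE is 0.200 for a single-stratum contrast and 0.141 for an averaged one. These correspond to s√(2/55) and s√(2/110) with s about 1.05, slightly above 1 because of the titre grouping.

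- b_R: 0.50/0.200 = 2.50; Φ(0.855) = 0.80 and Φ(0.54) = 0.71
- QIV-R vs QIV-C, infrequent: 0.25/0.200 = 1.25; Φ(-0.395) = 0.35 and Φ(-0.71) = 0.24
- QIV-R vs QIV-C, averaged: 0.35/0.141 = 2.48; Φ(0.84) = 0.80 and Φ(0.52) = 0.70

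**Dependence on b_R-add.** The averaged QIV-C contrast takes 0.10 of its 0.35 from b_R-add = 0.2. As a sensitivity check that is not a scenario in the plan, power at 55 per cell is 0.688 / 0.567 with b_R-add = 0.1, and 0.557 / 0.428 with b_R-add = 0.

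**The 74% figure.** The plan's two-sided column reads 0.712 at 55 and 0.741 at 60. The sentence follows 55 per cell and 330 in total (6 × 55), so the matching value is 71%. If 74% was meant for the 60 recruited, the plan's 10% attrition leaves 60 × 0.9 = 54 evaluable. Interpolating between the rows for 50 and 55 gives 0.665 + 0.8 × (0.712 - 0.665) = 0.70.

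**The case against.** The strongest reply is that the QIV-C wording in 13.2 is one loose phrase. Section 4.2.1 says the study is powered primarily against QIV-E, 13.3 says the same of its simulation, and 13.2 itself names a single recombinant-vaccine parameter. On the history-averaged reading, which best fits 6.1 and 13.2, QIV-R vs QIV-C does have about 80% one-sided power, so the figure in 13.2 happens to be right and the table is conservative for QIV-E. The 35% / 24% belongs to a contrast the plan never names. The meaning of b_R can be worked out from the coding, and the 74% slip is 3 points in a sentence that does not drive the sample size.

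Much of this is fair, and it limits the size of the problem: the sample size is not shown to be inadequate. It does not remove the problem. Section 4.2.1 agrees with 13.3, which leaves 13.2 as the outlier. A correct 80% for QIV-C would be a coincidence of an unreported calculation, and it rests on the assumed interaction. The reading that gives 35% cannot be set aside either, because 13.4.1 points to the interaction model and to a test on a model parameter, and in that model the averaged contrast is a combination of parameters.

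It is also true that a history covariate (13.4) is compatible with the 13.3 model, and that 13.4.4 concerns a secondary objective. The gap is that no section names the primary contrast. Naming it is a decision about the primary analysis and therefore the sponsor's to make. The synopsis adds to the uncertainty by specifying mixed-effects linear regression for the same analysis.

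**Conclusion.** The concern holds in all three parts and should be fixed.

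- The power stated in 13.2 for QIV-R vs QIV-C has no reported calculation behind it. At 55 per cell it is about 80% / 70% (one-sided / two-sided) for the history-averaged contrast and about 35% / 24% for the infrequent-stratum contrast.
- The table in 13.3 is power for QIV-R vs QIV-E in the infrequently vaccinated (81% / 71% at 55). For the history-adjusted difference in 6.1 the corresponding power is over 99% one-sided and about 99% two-sided.
- Two-sided power at 55 per cell is 71%, not 74%.

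These figures take the plan's parameters and titre coding as given. The averaged QIV-C figure is the most fragile: it falls to about 56% one-sided if the QIV-R interaction is 0 instead of 0.2.

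**What to change.** 1. In 13.3, replace 74% with 71% for 55 per cell, or state that 74% applies to 60 per cell with no attrition.
2. In 13.4.1, name the history-averaged contrast as the primary test for both comparisons, in line with 6.1 and 13.2: b_R + b_R-add/2 for QIV-R vs QIV-E, and (b_R - b_C) + (b_R-add - b_C-add)/2 for QIV-R vs QIV-C. Bring the synopsis's description of the model into line.
3. In 13.2 and 13.3, restate power for these contrasts at 55 per cell: over 99% / about 99% against QIV-E and about 80% / 70% against QIV-C, noting that the latter depends on b_R-add = 0.2. Label the existing table as infrequent-stratum power.
4. In the 13.3 term table, describe b_R and b_C as effects in the infrequently vaccinated.

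If the sponsor prefers to keep the infrequent-stratum parameter, 13.2 should limit the 80% / 71% statement to QIV-R vs QIV-E and give about 35% / 24% for QIV-R vs QIV-C.

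The cost is text changes in 13.2, 13.3, 13.4.1 and the synopsis, a relabelled table, and a few extra figures from the existing simulation. The choice of contrast should be recorded before outcome data are compared by arm. The stated two-sided power falls by 3 points, and no extra participants are needed.
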